2.1 Background and Rationale

Even before the onset of the current civil war, Yemen was one of the poorest countries in the world ranking 183 out of 191 countries and territories on the UN Human Development Index. The World Food Programme (WFP) estimates that currently 17 million Yemeni (half the population) are food insecure and 2.2 million preschool children are acutely malnourished (World Food Programme, 2023a). In 2022, 17% of school children in Yemen received school meals (WFP, 2022) and in 2023, the humanitarian response will cover only 8% of the needs of education sector, leaving it with the second highest unmet need (OCHA, 2023). WFP provides nutritious snacks (imported or locally procured), either fortified date bars or fortified high energy biscuits, to 1.55 million school children. There is an urgent need to understand how to improve access to nutritious school meals to support students and schools throughout the country.

2.2 Objectives and hypotheses

The aim of this study is to evaluate the effectiveness and cost-efficacy of adding a daily drink of milk to an ongoing school feeding program to improve children's diet.

3. Study methods

3.1 Trial design

In this cluster randomized controlled effectiveness trial, 42 schools in Al Mhuka district, Taiz Governorate, Yemen were randomly assigned to one of two groups: (1) Standard of care (control) group, which WFP's school feeding program involving daily distribution of high energy biscuits (n=20); and (2) School milk (intervention) group, which received the standard of care intervention with the addition of a daily drink of milk. A baseline survey was conducted prior to the start of the milk distribution in November 2023. An endline survey was conducted at the end of the school year in May 2024.

3.2 Recruitment

The primary reference group for this study is primary school aged children enrolled in schools supported by the school feeding program. A secondary reference group includes their caregivers. Lists of currently enrolled children were obtained from each school at the start of the school year. Children were randomly selected for participation in the survey, where the selection was stratified by gender.

3.3 Eligibility (inclusion / exclusion criteria)

Inclusion criteria

- Children enrolled at baseline in schools involved in the study
- Adult caregivers (≥18 years of age) of children included in the study

Exclusion criteria

• Household head, child, parent or guardian unwilling to participate in the study

The original intent to limit eligibility to children aged 6-8 y at baseline was dropped at enrolment due to the small number of children available in this age group in each school.

3.4 Randomization

A list including 42 eligible schools in the targeted districts was obtained from the Ministry of Education by in-country implementation partners. Data on school enrolment was used to classify the targeted schools into tertiles of school size. The 42 schools (clusters) were then allocated to the two study groups using a simple randomisation procedure performed in Stata, with randomisation stratified by school size tertile. The original intent of using restricted randomisation to allocate schools to interventions was abandoned due to the unavailability of school level data prior to the baseline and the need to allow implementers to plan for implementation roll-out as soon as the baseline survey was completed.

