4.2 Analysis of attrition

Attrition rates will be presented by intervention arm using a CONSORT diagram. We will test for differences between attrited and non-attrited children at baseline using t-tests in terms of the characteristics described in 4.1 above. T-tests will be considered significant at p<0.05. If significant differences are found, we will perform attrition analyses using inverse probability weighting.

5. Adherence, protocol deviations, and analysis sample

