8.3 Statistical analysis plan for each hypothesis

We will a single difference model specification of the following form:

$$Y_{i1} = \beta_0 + \beta_1 T_i + \beta_2 Y_{i0} + \varepsilon_i$$

where Y_{i0} is the outcome variable at baseline, Y_{i1} is the outcome variable at endline and T_i is a dummy variable for the treatment. This (ANCOVA) estimator has been shown to provide more efficient estimates of program impact than difference-in-difference estimators when autocorrelation of outcomes is low (4). To account for c-RCT design and the level of clustering of the outcome under analysis, we will employ linear multi-level regression models. The multi-level models will use both fixed effects with dummy variables for each intervention and random effects at the school level (unit of randomisation) to take into account clustering and to estimate the standard error in an unbiased manner. Alternative fixed effect models with standard errors clustered at the school level will also be considered. Primary analyses will be unadjusted for baseline covariates. In addition to the unadjusted primary analyses, we will report adjusted estimates, conditional on the covariates described in 7.2 above. We will use linear multi-level regression models and estimate mean differences for continuous outcomes and risk differences for binary outcomes. Alternative log-binomial and log-Poisson models will be considered for binary outcomes.

The same model will be repeated with the addition of an interaction term to assess effect modification for the variables listed in 7.3 above.

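### The primary ANCOVA omits child age, sex and grade, although children may have entered after schools were allocated and the age limit was dropped at enrolment

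*SAP*

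**What the plan says.** **Allocation.** In section 3.4 the only data named as an input to allocation are enrolment counts: "Data on school enrolment was used to classify the targeted schools into tertiles of school size". Restricted randomisation was given up "due to the unavailability of school level data prior to the baseline and the need to allow implementers to plan for implementation roll-out". Section 3.1 adds that "A baseline survey was conducted prior to the start of the milk distribution in November 2023". No section gives the date of allocation.

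**Entry of children.** Section 3.2: "Children were randomly selected for participation in the survey, where the selection was stratified by gender". Section 3.3 lists one exclusion: "Household head, child, parent or guardian unwilling to participate in the study". The same section reports that the 6-8 y limit "was dropped at enrolment due to the small number of children available in this age group in each school". Section 7.3 now names age groups of 6-9, 10-14 and 15-18 y.

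**Analysis.** Section 8.3 regresses the endline outcome on treatment and the baseline outcome, and states: "Primary analyses will be unadjusted for baseline covariates". Estimates adjusted for the covariates of 7.2, which include child age, sex and grade, are reported in addition. Section 7.2 calls those covariates confounders and says they were chosen in advance.

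**Losses.** Section 4.2 plans a CONSORT diagram by arm and a comparison from baseline onward: "We will test for differences between attrited and non-attrited children at baseline".

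**The concern.** Randomising schools balances the arms in expectation only if the entry of individual children does not depend on the arm. Where schools are allocated first and families agree later, that condition can fail, and the protection then rests on knowing who declined and on adjusting for what was measured.

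The point has two parts here. First, the order of allocation and consent is left open, and the available wording leans towards allocation first. Second, the sample now spans a much wider age range than intended, with few schools per arm, so age and grade can differ between arms even if nothing went wrong at entry. The SAP has already chosen and collected the variables that would deal with such a difference, but the headline estimate does not use them. It also does not say what follows if the primary and adjusted estimates disagree.

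**Working it through.** **1. What the text supports on timing.**
- Missing school data before baseline is given as a reason for the choice of randomisation method. That reason would carry no weight had allocation waited for baseline data.
- Section 3.4 adds that implementers needed to plan so that roll-out could begin once the baseline survey was finished. This also points to allocation before or during the survey.
- No date is given for allocation, child selection or consent. Allocation before baseline is a fair inference. That families knew the arm when they agreed is not stated anywhere.

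**2. Routes by which entry could differ by arm.**
- Selection of children: random from school lists, stratified by gender. Little room for recruiter choice.
- Dropping the age limit: the reason given is few children in each school, with no sign of a difference by arm. Its effect is to widen the age range, which makes any imbalance in age more consequential.
- Refusal or non-enrolment: open, and not examined by arm in the plan.

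**3. The plan's own figure.** Inputs from section 3.5: 20 schools per arm, m = 30 children per school, ICC = 0.05. Two-sided 5% comes from section 8.1. Power is not stated, and 80% is assumed.
- Design effect = 1 + (30 - 1) x 0.05 = 2.45
- SE = sqrt(2.45/30 x (1/20 + 1/20)) = 0.0904 SD
- Detectable effect with t quantiles on 38 df = 0.260 SD (0.253 SD with normal quantiles)

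The stated 0.26 SD is reproduced. At 90% power the result would be 0.29 to 0.30 SD, which does not match.

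**4. Illustration of a shift from refusal.** The SAP gives no refusal rates, so every input here is assumed. If a share r of an arm refuses, and participants differ from refusers by d, the participant mean departs from that of all sampled children by r x d. The shift in the arm contrast is then (r1 - r0) x d in size. With d = 0.5 SD and 5% refusal in one arm:

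| Refusal in the other arm | Shift (SD) | Share of 0.26 SD |
|---|---|---|
| 5% | 0 | 0% |
| 10% | 0.05 x 0.5 = 0.025 | 10% |
| 15% | 0.10 x 0.5 = 0.05 | 19% |
| 20% | 0.15 x 0.5 = 0.075 | 29% |

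**5. Consequence for the test if a shift b remained in full.** Two-sided error = 1 - Phi(1.96 - b/0.0904) + Phi(-1.96 - b/0.0904), using the SE from step 3 with no gain from the baseline outcome:
- b = 0.02: about 5.6%
- b = 0.05: about 8.6%
- b = 0.10: about 19.8%

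**6. Effect of the baseline term.** If the same shift b is present at baseline and endline, ANCOVA with baseline coefficient beta leaves b x (1 - beta). The residual runs from all of b when beta = 0 to none of it when beta = 1. The figures in steps 4 and 5 are therefore upper values for the assumed inputs. The SAP does not report the baseline-endline correlation. Its remark on low autocorrelation is a general condition for the efficiency of ANCOVA, not a result for these data.

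**The case against.** A reader might infer that the trial has recruitment bias because enrolment and refusal followed an unblinded allocation. The document does not support that. Consent is undated, nothing says that families or recruiters knew the arm, and the baseline survey preceded milk distribution, so nobody could see milk when deciding whether to join. Concealment and consent procedures are commonly left to the protocol, so silence in the SAP is not evidence. This objection stands in full.

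A reader might also infer that the age change was selective, or that the primary analysis makes no adjustment at all. Neither holds. The reason for the age change is trial-wide, and children were drawn at random. The primary model contains the baseline outcome, adjusted estimates are reported, and section 4.1 tabulates age, sex and grade by arm, so an imbalance would be seen.

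Two further objections concern the remedy. Adjustment for age, sex and grade does not correct selection on unmeasured willingness, which is true and limits what the change can achieve. And the endline survey is described as already conducted, so changing the primary model now could be criticised. That is why the change must come before any comparison of outcomes by arm and be recorded as an amendment. The covariates are pre-specified, which limits the room for choice.

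Finally, section 4.2 does not say where the CONSORT diagram starts. It may begin at sampled children; only the statistical comparison is tied to baseline. Reporting of refusals is thus a point of missing detail, not an error.

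**Conclusion.** The concern holds in a limited form. Allocation before baseline is a fair reading of section 3.4, and recruitment bias is possible but not shown. What is firm is that the age range was widened at enrolment, that the mix of age and grade can therefore differ between arms by chance or through refusal, and that the primary model leaves out variables which section 7.2 itself treats as confounders.

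The size is unknown. The 0.05 SD shift (19% of 0.26 SD) rests on assumed refusal of 15% against 5% and an assumed 0.5 SD difference, before any reduction from the baseline term. It is zero if refusal does not differ by arm. Nor does it measure what the proposed adjustment would remove, since that acts only on imbalance in age, sex and grade.

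The change is an inexpensive improvement, not the repair of a demonstrated bias. Any gain in precision depends on how strongly these variables predict the outcome. It is most plausible for the raw cognition and learning scores, which section 6.2 standardises for age and sex only if the distributions allow, and is not established for the two primary outcomes.

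**What to change.** **Section 8.3.** Before outcomes are compared by arm, define the primary model as the endline outcome on treatment, baseline outcome, child age, sex and grade, with the school random effect as planned. Keep the model without these three covariates as a supporting analysis. Record the change and its date in section 9. State that age and grade both stay in the model, since the rule in section 8.5 would otherwise allow one to be dropped as collinear.

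**Section 4.2 (minor, reporting).** Begin the CONSORT flow at children sampled from the school lists and show refusals by arm. Adding the dates of allocation and consent would settle the timing question; if consent came first, the concern about entry after allocation falls away.

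**Cost.** A change of SAP wording. The covariates are already listed and collected, and an adjusted model is already planned. The headline estimate would depend on the imputation rule of section 8.2 wherever age, sex or grade is missing. The change does not remove selection on unmeasured willingness to join.

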3.5 Sample size, power, and detectable difference

Power calculations based on available clusters in targeted districts and resource availability suggested 20 clusters (schools) per intervention arm and 30 households (with index children) per cluster. The primary outcomes of the trial include the 10-food group dietary diversity score in primary school children. For this outcome, assuming an inter cluster correlation coefficient (ICC) of 0.05, a sample size of 30 children per school leads to a minimum detectable effect size (MDES) of 0.26 SDs.

4. Sample characteristics

4.1 Baseline characteristics

The following variables will be presented to describe the characteristics of the study sample. They will be presented by intervention arm.

Variable	Definition
Child age	Age in years
Child sex	Male vs female
Child grade	Current grade in school
Caregiver age	Age in years of primary caregiver
Caregiver education	Level of education of primary caregiver: no formal education complete, primary complete, secondary complete, higher complete. Depending on the distribution we will also create an indicator for any formal education vs none.
Household head age	Age in years of head of household
Household head occupation	Primary occupation of the head of household
Household wealth	Wealth quintile, derived from a wealth index, which will be derived hosing
quintile	characteristics and asset ownership using Principal Components Analysis
Household size	Total number of household members

4.2 Analysis of attrition

Attrition rates will be presented by intervention arm using a CONSORT diagram. We will test for differences between attrited and non-attrited children at baseline using t-tests in terms of the characteristics described in 4.1 above. T-tests will be considered significant at p<0.05. If significant differences are found, we will perform attrition analyses using inverse probability weighting.

5. Adherence, protocol deviations, and analysis sample

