8.1 Framework, confidence intervals and p-values

All tests will be two-sided, at 95% confidence interval and a 5% significance level unless otherwise indicated (i.e., interaction analyses). No adjustments will be made for multiple hypothesis testing (3).

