8.2 Missing data

Missing data on any covariates will be imputed using mean cluster imputation if <5% of data is missing and multiple imputation if $\ge5\%$ of missingness. Missing data on outcomes will not be imputed.

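### The inverse probability weighting in SAP 4.2 depends on t-tests of leavers against stayers with no arm term, a contrast that does not target differences between arms in who is lost

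*SAP*

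**What the plan says.** SAP section 4.2 sets the whole attrition procedure. The element shown by arm is the rate of loss: "Attrition rates will be presented by intervention arm using a CONSORT diagram". The comparison of who was lost is then defined: "We will test for differences between attrited and non-attrited children at baseline using t-tests in terms of the characteristics described in 4.1 above". The threshold is "T-tests will be considered significant at p<0.05", and the consequence is "If significant differences are found, we will perform attrition analyses using inverse probability weighting".

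Section 4.1 lists nine characteristics: child age, sex and grade; caregiver age and education; household head age and occupation; wealth quintile; household size. Baseline outcomes are not among them. Section 4.2 states no arm term, no allowance for school clustering and no number of significant tests needed. Section 8.1 adds "No adjustments will be made for multiple hypothesis testing". On missing endline values, section 8.2 says "Missing data on outcomes will not be imputed".

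Section 8.3 matters for how far the point reaches. The primary model contains treatment and the baseline value of the outcome. A second model, always reported, adds the covariates of section 7.2, which are the same nine variables.

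**The concern.** Attrition biases a randomised comparison when the children who remain differ between arms. A test of leavers against stayers over the whole sample asks whether loss is selective on average, which is a different question. Suppose poorer children drop out of control schools and better-off children drop out of milk schools. The two patterns then offset each other in the pooled test, while the completers in the two arms move apart.

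The trigger decides whether the one analysis designated for attrition is done at all. A rule that can stay silent in the harmful case, and often fires in the harmless one, is a weak basis for that decision.

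Two details of the tested list add to this. The baseline outcomes, which bear directly on the endline outcomes, are left out. Household head occupation is nominal, so a t-test does not apply to it unless it is recoded.

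**Working it through.** **The plan's own figure.** Section 8.5 gives none for attrition, and neither does section 4.2; the yardstick used here is the detectable effect of 0.26 SD in section 3.5 (20 schools per arm, 30 children per school, ICC 0.05). Design effect = 1 + 29 × 0.05 = 2.45. With two-sided 5%, 80% power (assumed, as power is not stated) and 38 degrees of freedom: (2.024 + 0.851) × √(2 × 2.45/600) = 0.260 SD. The figure reproduces.

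**Assumed inputs.** The SAP gives no attrition rate, selection strength, wealth-outcome correlation or outcome autocorrelation. The values below are assumptions: 20% loss in each arm, leavers 0.5 SD from their arm's mean wealth, wealth-outcome correlation 0.3 at both visits, outcome autocorrelation 0.3 to 0.5, arms of equal size.

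**Selection in opposite directions.**
- Shift of completers in each arm: 0.2 × 0.5/0.8 = 0.125 SD, in opposite directions.
- Pooled means: leavers (0.5 − 0.5)/2 = 0; stayers (0.125 − 0.125)/2 = 0. The pooled difference is 0.
- Wealth gap between the arms' completers: 2 × 0.125 = 0.25 SD.
- Raw outcome bias: 0.25 × 0.3 = 0.075 SD. The completers' baseline outcomes differ by the same amount.
- Primary ANCOVA, taking the slope on the baseline outcome as the autocorrelation r: bias ≈ 0.075 × (1 − r). At r = 0.3 this is 0.0525 SD, and 0.0525/0.26 = 20%. At r = 0.5 it is 0.0375 SD, and 0.0375/0.26 = 14%. Simulating the scenario gives about 0.054 and 0.040 SD.
- Adjusted model with wealth in quintiles (simulated): about 0.007 SD remains, and 0.007/0.26 is just under 3%.

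**The same selection in one arm only.**
- Pooled leavers: 0.5/2 = 0.25. Pooled stayers: −0.125/2 = −0.0625. Difference: 0.3125 SD.
- With 240 leavers and 960 stayers, the standard error is √(1/240 + 1/960) = 0.0722, so z = 0.3125/0.0722 = 4.33 and power is Φ(4.33 − 1.96) ≈ 99%.

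**How well the trigger discriminates.**
- No selective attrition, nine independent tests: 1 − 0.95⁹ = 37% chance that at least one is significant. Simulation with 40 schools of 30 and 15% loss gave 36%, or 38% when covariates and attrition both have ICC 0.05.
- Opposite selection, simulated with 10-30% loss and a latent correlation of 0.3-0.5 between the driving covariate and loss: the pooled t-test on that covariate was significant in 4-9% of runs without clustering and 5-13% with ICC 0.05. At least one of nine tests was significant in 37-43%.
- In the same runs an arm-by-attrition interaction test on the driving covariate was significant in 100%.

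The chance that the trigger fires is therefore almost the same with harmful, offsetting selection as with none.

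**The case against.** The strongest reply is that the SAP does not lean on IPW alone. A reader might infer from section 8.2 that conditional IPW is the only protection against missing endlines. Section 8.3 does not support that: the baseline outcome is in the primary model, and the model adjusted for all nine covariates is reported whatever the t-tests show. If loss is driven by one of those covariates, the adjusted estimate removes most of the bias. This stands. It is also why the raw 0.075 SD (29% of 0.26) should not be quoted as the bias, since no outcome model in section 8.3 omits the baseline outcome.

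A reader might also infer that the test misses any attrition that differs by arm. It does not. It is blind when selection nearly cancels across arms. Selection of the illustrated strength in one arm would be found about 99% of the time, and a difference in rates would be visible in the CONSORT diagram. Even with offsetting selection, IPW may still be done because another of the nine tests happens to be significant.

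Third, firing by chance does little harm, because it only adds an analysis that the fix would always run. That stands too. The 37% shows that the rule discriminates poorly, not that it invalidates anything. It also assumes independent tests; child age and grade are plainly related, which would lower it. Larger figures need a covariate ICC that the SAP does not give.

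Finally, a t-test on child sex, a binary variable, is acceptable at this sample size. The objection to the type of test is confined to occupation.

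**Conclusion.** The point holds as a weakness in a robustness check, not as a flaw that undermines the primary analysis. The trigger as written does not test for a difference between arms in who is lost. It can be silent when selection is opposite in the two arms, and it fires about as often when there is no selective attrition.

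In the illustration the primary ANCOVA keeps a bias of about 0.04-0.05 SD, roughly 15-20% of the detectable effect. That rests on assumed loss, selection and correlations, and on exact offsetting, which is the worst case for the pooled test. Most of it goes in the adjusted model if the driver is one of the nine covariates.

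That the tests are pooled over arms and ignore clustering is the plain reading of section 4.2, but it is inferred from what the section leaves unsaid. Section 8.3 shows that the plan handles clustering in the outcome models, so the SAP does not support a claim that clustering is neglected throughout.

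**What to change.** In section 4.2, remove the significance trigger. Always report an IPW sensitivity analysis for the primary outcomes, with a prespecified retention model containing arm, baseline outcome, the section 4.1 characteristics, school-size tertile and a limited set of arm-by-characteristic terms (at least baseline outcome and wealth). Enter occupation as categories.

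Report attrition rates by arm, and the arm-by-characteristic comparisons, with school-clustered standard errors. Treat them as descriptive, so that no p-value decides whether an analysis is done.

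The cost is a change of SAP wording and one extra analysis on data already collected. The downside is somewhat more variable weights, which is the reason for keeping the interaction terms few.
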